4.3 MAIN AND SECONDARY VARIABLES

Main study variables: improvement in the recognition of basic emotions, social cognition, emotional intelligence and social competence.

Secondary variables: improvement in symptoms and work results.

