2 INTRODUCTION

Interpersonal relationships are paramount to achieve adequate performance and conservation of various social roles that individuals have to cover throughout their life, which in turn becomes a determining factor for their social integration and adaptation in the long-term. For this reason, people need a number of cognitive, behavioral and emotional skills that allow and facilitate cohabitation and social exchange.

Schizophrenia is a disorder characterized by the presence of deficits in social and interpersonal functioning, being these key elements in its definition, in addition to involving a source of stress for the

patients and contributing to relapses and the exacerbation of symptoms¹, also generating enormous personal, socio-family, healthcare and economic costs².

In recent decades hundreds of investigations have focused on the study of these non-social cognitive deficits, such as executive functioning, attention or memory³, but in recent years researchers have also included the study of social cognition⁴. The reason lies in the fact that social cognition was included in the list of key cognitive deficits in schizophrenia, largely due to the appearance of empirical evidence that relates social cognition to social functioning^{5,6} and that assigns it a role of mediating variable between basic social cognition or neurocognition and social functioning^{7,8}.

From an operational point of view, we can classify the skills and functions involved in the regulation of social behavior into two categories:

- Social skills⁹, a construct that includes activities such as:
 - Communicate our needs and thoughts.
 - Listen, understand and respond appropriately to other people.
 - Produce and interpret nonverbal communications.
 - Adapt eye contact, facial expressions and body language to social interaction.
 - Regulate our emotions during them.
- Social cognition¹⁰, a construct that includes activities such as:
 - Perception of emotions, both in faces and in people's voices.
 - Social perception, that is, the interpretation of a series of clues about what happens in a given social context and applying social knowledge to develop the most appropriate behavior for said context.
 - Theory of Mind (ToM), understood as the ability we have to realize that others have ideas and intentions different from ours and that allows us to behave with these people in an appropriate way.

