 - Attributive style, understood as the tendency that individuals have to explain the events that happen to them in life and that often leads to considering negative events as caused by the bad intentions of others.

People with schizophrenia tend to isolate themselves, showing little initiative and motivation towards activities, especially social ones, than before the onset of the illness. They suffer from social isolation because they find it difficult to establish contact with other people and carry on a conversation, they have difficulty functioning normally under stressful conditions, in part due to their difficulties in social skills and problem solving.

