3 OBJECTIVES AND PURPOSE OF THE STUDY

3.1 MAIN OBJECTIVE

Assessing the efficacy of a cognition and social competence training program (e-Motional Training) in patients with schizophrenia in improving basic emotion recognition, social cognition, emotional intelligence and social competence.

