4 METHODS

4.1 DESIGN

A single-blind randomized clinical trial (Annex I) will be carried out in patients suffering from schizophrenia and who have the legal capacity to consent. Study participants will be randomized to either the experimental group (e-Motional Training) plus Individual Placement and Support (IPS) or the control group (IPS alone).

Sample size calculation:

Taking as a reference the results of the pilot study in schizophrenia carried out by the research team in Galicia ([name] et al), where the average reached in the group before the intervention in the Stories of Theory of Mind by F. Happé in his Spanish version by Pousa (1999) was 8.5 points with a standard deviation of 3.61 points and where, after the intervention, the mean score achieved was 11.67 and the standard deviation was 4.72, for a power of 80% and a confidence level of 95%, the necessary sample in each group would be 30 patients, assuming losses of 5%. An attempt will be made to obtain a total sample of 80 people, taking into account losses during follow-up.

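### Four unranked main domains have no designated score, success rule or multiplicity method, and the sample size covers one unadjusted test on the theory-of-mind stories only

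*Protocol*

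**What the plan says.** - **Main outcomes.** Protocol 4.3 gives "Main study variables: improvement in the recognition of basic emotions, social cognition, emotional intelligence and social competence". Protocol 3.1 sets the main objective as efficacy "in improving basic emotion recognition, social cognition, emotional intelligence and social competence". The SAP repeats the four domains after naming its methods. None is ranked. The next line of 4.3 adds "Secondary variables: improvement in symptoms and work results".
- **Instruments.** Protocol 4.4 lists nine. Read with section 2, most can be linked to a domain: the 60 Faces Test to basic emotions; MSCEIT to emotional intelligence; and MASC, Hints, Faux Pas, the theory-of-mind stories and AIHQ to social cognition. AIHQ belongs there because section 2 includes "Attributive style, understood as the tendency that individuals have to explain the events" in that construct. The Social Functioning Scale for social competence is an inference. Section 2 also puts "Perception of emotions, both in faces and in people's voices" under social cognition, so two of the four main domains overlap.
- **Analysis.** Protocol 4.6 names only the software. The SAP names mixed models with pre and post measurements, an independent-samples t-test and Levene's test. It attaches none of them to a score.
- **Sample size.** Protocol 4.1 starts from "the average reached in the group before the intervention in the Stories of Theory of Mind", 8.5 (SD 3.61), and continues "after the intervention, the mean score achieved was 11.67 and the standard deviation was 4.72". It concludes that "for a power of 80% and a confidence level of 95%, the necessary sample in each group would be 30 patients", with 5% losses. The target is 80 in total. Sidedness is not stated.

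**The concern.** Nothing in the plan fixes which result would meet the main objective. With four domains, five candidate instruments in one of them and two analysis methods, that choice could be made after the data are seen. No later analysis can restore pre-specification.

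The missing rule matters in opposite directions. If any one domain is enough, the false-positive rate rises above 5%. If all four are required, the error rate is protected but the sample size was not worked out for that demand. The only power statement in the plan concerns one instrument that 4.3 does not name.

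**Working it through.** **1. The plan's own figure.** Inputs from Protocol 4.1: means 8.5 and 11.67, SDs 3.61 and 4.72, power 80%, confidence 95%, losses 5%.

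- Difference: 11.67 − 8.5 = 3.17.
- Root-mean-square SD: √((3.61² + 4.72²)/2) = 4.20. Standardised effect: 3.17/4.20 = 0.754.
- n per group = 2 × [(1.96 + 0.842) × 4.20/3.17]² = 27.6, so 28. Then 28/0.95 = 29.5, so 30. This matches the plan.
- A one-sided 5% test with the post SD also matches: 2 × [(1.645 + 0.842) × 4.72/3.17]² = 27.4, so 28, then 30.

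Both routes are one unadjusted test on one score. The 3.17 is a change within a single pilot group used as a between-group difference, so the result is valid only if controls do not change. Below, 28 per arm is the evaluable number behind the stated 30. The target of 80, split 1:1 (assumed), gives 40 × 0.95 = 38.

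**2. If any domain counts.** One score per domain at two-sided 5%. If independent: 1 − 0.95⁴ = 0.185. With equal correlations between scores (assumed), by numerical integration:

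| Tests | corr. 0 | corr. 0.5 | corr. 0.7 |
|---|---|---|---|
| 4, either direction | 0.185 | 0.156 | 0.130 |
| 4, false benefit only | 0.096 | 0.078 | 0.065 |
| 8 (all instruments except PANSS; inferred count) | 0.337 | 0.250 | 0.191 |

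One two-sided 5% test has a false-benefit rate of 2.5%. The five social cognition instruments alone give 0.209, 0.183 and 0.148 at correlations 0.3, 0.5 and 0.7.

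**3. If all four must succeed.** No error inflation with one fixed score each. Power was simulated, assuming the plan's effect in every domain, no control change, complete data and between-domain correlation 0 to 0.7.

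- Post-score comparison: 39–61% at 28 and 66–78% at 38 per arm.
- Group-by-time term, change SD = √(3.61² + 4.72² − 2r × 3.61 × 4.72), where r is the pre-post correlation, at 38 per arm: about 37–77% for r = 0.3 to 0.5; 92–95% for r = 0.7; 99% for r = 0.8. At 28 per arm with r = 0.8: 94–96%.

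**4. One primary score, two-sided 5% (noncentral t).** Post-score comparison: 79% at 28 and 90% at 38. With an assumed control gain of 1 point, so a difference of 2.17: 48% and 60%. For the group-by-time term:

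| r | SD of change | Power at 28 | Power at 38 | At 28, controls gain 1 point | At 38, controls gain 1 point |
|---|---|---|---|---|---|
| 0.3 | 5.01 | 64% | 78% | 36% | 46% |
| 0.8 | 2.84 | 98% | 99.8% | 80% | 91% |

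**5. Four co-equal domains with adjustment.** Post-score power per domain, effect present in all four. Holm: 68–71% at 28 and 84–87% at 38. Fixed alpha 0.05/4 = 0.0125: 60% and 76%.

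**The case against.** - **The sizing shows that the stories are primary.** It is the best clue to intent, and it is why the stories are the natural choice in the fix. But 4.1 never calls them primary and 4.3 does not mention them.
- **The four domains are joined by a conjunction, so all must succeed and no adjustment is needed.** The wording fits this at least as well as the any-domain reading, and the error rate would then be protected. But it is not stated as a rule, no score is named for any domain, and 4.1 does not size for it.
- **The target of 80 leaves room.** For power this partly stands: Holm reaches 84–87% per domain at 38 per arm for post scores. It does not settle what counts as success.
- **The plan does link instruments to domains.** Largely true. What is missing is the designated score, and the choice is widest within social cognition.

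A reader might go further and infer that 95% confidence and 80% power cannot both hold under either success rule. The documents do not support that. Under the all-four rule error is not inflated, and with the group-by-time term at a pre-post correlation of 0.7 or 0.8, power at 38 per arm is above 90%. The documents give no pre-post correlation, so neither adequate nor inadequate power can be concluded. They also attach the 80% and 95% to the stories alone, so there is no four-domain claim to refute.

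**Conclusion.** The concern holds as a missing specification and should be corrected before analysis. The sections where a primary score, success rule and multiplicity method belong (3.1, 4.3, 4.6 and the SAP) are present, and they contain none of these. Under an any-domain rule the family-wise error would be 13–19% for four scores, and more if several instruments per domain are tested. Under an all-four rule the issue is power, which runs from well below 80% to well above it depending on the test and on a pre-post correlation that the plan does not give.

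The multi-domain figures assume equal effects in every domain and the correlations stated; the documents give effect data for the stories only. All power figures assume no control change unless a gain is shown. That assumption affects the group-by-time term as well as the post-score comparison.

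**What to change.** Before any outcome data are examined, amend 3.1, 4.3, the sample-size paragraph in 4.1 and the SAP in one of two ways.

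1. **Single primary (consistent with the present sizing).** Name the theory-of-mind stories as the primary score, tested at two-sided 5% by the group-by-time term of the SAP's mixed model, with the t-test supportive only. Name one score for each of the other domains as a key secondary with a stated multiplicity method, for example Holm after a significant primary. Report the remaining scores as exploratory.
2. **Four co-equal domains.** Name one score per domain, state either Holm or an all-four rule, and restate power for that rule.

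In both options, restate the sizing for the chosen test with its sidedness, assumed pre-post correlation and assumed control-arm change.

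The cost is text only, with no extra visits or assessments. The downsides are that a significant non-primary score can no longer be presented as the main result, that option 1 moves three domains to key secondary, and that the restated power may fall below 80% under either option.

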4.4 DATA COLLECTION

For the pre- and post-training averages, the following instruments will be used:

- *Hints Test*: it is the Spanish adaptation of Gil et al. of the Hitting Task¹¹, a test created by Corcoran et al. This test includes ten short stories, in all of them two characters appear, and at the end of each one, one of the characters drops a hint. The subject is asked what the character in the story really meant by the comment they made. The ability to infer the real intention of the speaker, underlying this indirect use of language, implies the use of ToM.
- *Faux Pas*¹²: it is a widely used test to evaluate ToM, it consists in understanding socially embarrassing situations, in which one of the characters involuntarily says or does something

inappropriate or incorrect. After this short story, the patient is asked several questions: a control question; another one for blunder detection and others for blunder comprehension; finally, there is a question that measures empathic understanding.

- *F. Happé's theory of mind test* (adapted by Pusa 1999)¹³: these are stories that use figurative language, not literal, the characters are ironic, lie or tell white lies. In one of the stories, the character says something that should not be understood in a literal sense, and the subject is asked to explain why the character says that.
- *Ekman 60 Faces Test*¹⁴: 12 photographs of actors showing one of the six basic emotions (sadness, anger, fear, disgust, surprise and happiness), two of each emotion, one played by a man and one by a woman. Participants are asked to choose the appropriate verbal label to describe what the actor in the photograph was feeling.
- *Ambiguous Intentions Hostility Questionnaire (AIHQ)*¹⁵: evaluates cognitive social biases based on different comic strips in which a series of situations are presented in which the intentions of the characters are ambiguous. The participant is asked to rate on a Likert scale why they think the protagonist acts in this way (AIHQ HB subscale, the hostility score), whether the other person has done the action on purpose (AIHQ IS subscale, the intentionality score) and how much they would blame them (AIHQ BS subscale, guilt score). Additionally, it also rates how angry this situation makes the subject feel (AIHQ AS, the anger score) and how they would respond to this situation (AIHQ AB, aggressiveness score). Higher scores reflect more hostile, negative, personal, and aggressive attributions.
- *Mayer-Salovey-Caruso Emotional Intelligence Test (MSCEIT)*¹⁶: This allows an evaluation of general emotional intelligence based on the subject's performance. It is made up of 141 items and the duration of its completion varies between 30 and 45 minutes, approximately.
- *Movie for the Assessment of Social Cognition (MASC)*¹⁷: the Spanish version of Lahera (2014) will be used. In this test, the subject must understand the various interactions established between the four characters and is asked about them through 40 multiple-choice questions. Questions include jokes comprehension, double meanings, innuendos, easily expressed emotional reactions, nonverbal cues or blunders. The test gives a social cognition score, but it also allows classifying the predominant type of error (hypo-mentalization, or a tendency to infer less social meaning than there is, or hyper-mentalization, or a tendency to over attribution).
- *Positive and Negative Symptom Scale (PANSS)*¹⁸: It consists of 30 items that evaluate the schizophrenic syndrome from a dual perspective; a dimension that evaluates the severity of the positive syndrome, the negative syndrome and the general psychopathology of the schizophrenic disorder; and another category that classifies it as positive, negative or mixed.
- *Social Functioning Scale (SFS)*¹⁹: This is a reliable instrument, specifically designed for the evaluation of the social functioning of people with schizophrenia. It is useful for researchers and clinicians interested in the variables involved in social functioning and, particularly, for those who work in family interventions or other psychosocial intervention programs in schizophrenia. It is composed of seven subscales: isolation/social integration, interpersonal communication, independence-execution, interdependence-competence, free time, prosocial activities, employment/occupation.

4.5 SAMPLE COLLECTION AND HANDLING

100 people with severe mental disorder will be selected. All records will be made anonymously, assigning each patient an identification number. All data will be kept for 5 years.

4.6 STATISTICAL ANALYSIS OF DATA

All data will be analyzed with the SPSS program.

5 WORK PLAN

The purpose of this study is to assess the efficacy of a multicomponent social skills training program in people with schizophrenia.

The expected duration of the study will be one year and will be carried out at the Sinpromi center. Participants will be randomly assigned to receive employment support (IPS control group) or employment support with cognitive rehabilitation (ET + IPS experimental group).

The experimental group (e-Motional Training + Individual Placement and Support) will receive a total of twelve sessions (one hour and a half per week for four months) for training. The training program will consist of the individual practice of tasks related to social skills through the use of an interactive video game, using a computer. During the training, a member of the research team will be present to answer questions. This program has been developed and initially tested by the Psychiatry Service of the Hospital Complex in Ourense.

To assess the level of social cognition, both groups will perform an evaluation before and after rehabilitation to determine whether the intervention has been advantageous or not (blinded investigator).

In addition, once the rehabilitation is finished, the two study groups will be searched for employment and all their variables will be analyzed, such as hours worked, maintenance, salary, etc.

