Statistical analysis plan

Online Training Program on Social Cognition for Patients With Schizophrenia

NCT ID not yet assigned

ULaguna
18-12-2019

Study title: TRAINING IN COGNITION AND SOCIAL COMPETENCE IN PATIENTS WITH SCHIZOPHRENIA

A single-blind randomized clinical trial will be carried out in patients suffering from schizophrenia and who have the legal capacity to consent to the study. Study participants will be randomized to either the experimental group (e-Motional Training) plus Individual Placement and Support (IPS) or the control group (IPS alone).

For data analysis, taking into account that not all patients will have pre and post information, general mixed models will be used with identification of the subject and repeated time measurements (pre and post).

It will be carried out for the analysis of the mean tests as variance (t-student test of independent samples and Levene's test of equality of variances),

The efficacy of a training program in cognition and social competence (e-Motional Training) will be evaluated in patients with schizophrenia when improving the recognition of basic emotions, social cognition, emotional intelligence and social competence.

INFORMATION ON THE USE OF RESOURCES AND FUNDING

(mandatory compliance)

Do you need funding for this study?				YES		NO	X
Do you have required funding for this study?				YES	X	NO	
How many hours of your time during work hours will you dedicate to this study?				25%			
Do you have the material means (equipment, techniques, others...)?				YES	X	NO	
Where will the study take place?							
CONSULTING ROOM	DAY HOSPITAL		UICEC		HOSPITALIZATION	X	OTHERS SINPROMI
Will additional tests be performed outside of routine clinical practice?*				YES		NO	X
*If YES, indicate below:							
Use of biological samples:				YES		NO	X
*If YES, indicate their location below:							
SERVICE / DEPARTMENT: PSYCHIATRY SERVICE. ULL.							
COLLECTION				YES		NO	X
BIOBANK				YES		NO	X
Use of patient clinical data:							
Transfer of encrypted data (pseudonymized) outside the EU to the entities of our group, to service providers or to scientific researchers who collaborate with us				YES		NO	X

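### Hours, job maintenance and salary are recorded only after training, and neither method named in the SAP uses the baseline SFS employment/occupation score for them

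*Protocol*

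**What the plan says.** Better employment is one of two secondary objectives (Protocol 3.2), and work results are a secondary variable (Protocol 4.3). Their timing is given in Protocol section 5: after rehabilitation, "the two study groups will be searched for employment and all their variables will be analyzed, such as hours worked, maintenance, salary, etc".

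Protocol 4.4 opens its list of tests with "For the pre- and post-training averages, the following instruments will be used". No item on that list records hours, job tenure or pay. The list does include the SFS, whose seven subscales end with "free time, prosocial activities, employment/occupation".

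The SAP's data analysis paragraph names two methods: a mixed model with subject and time (pre, post), and a "t-student test of independent samples" accompanied by Levene's test. It links neither to a named outcome and lists no covariate. Protocol 4.6 adds only the software.

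**The concern.** A pre/post model needs a pre record. For hours, maintenance and salary the documents describe none, so of the two named methods only the unadjusted two-sample comparison can do any work. That comparison discards a work-related baseline measure which the trial already collects from both arms.

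What is at stake is some precision on a secondary objective, and a clear statement before the data are seen of how work results will be compared. The validity of the test is not in question.

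**Working it through.** **1. The plan's own sample size.** Protocol 4.1 gives a pilot pre score that "was 8.5 points with a standard deviation of 3.61 points", and afterwards "the mean score achieved was 11.67 and the standard deviation was 4.72".
- Difference: 11.67 − 8.5 = 3.17.
- Root-mean-square SD: √[(3.61² + 4.72²)/2] = √17.66 = 4.20.
- n = 2(1.960 + 0.842)² × 17.66 / 3.17² = 27.6, so 28 per group; 28/0.95 = 29.5, so 30.

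This reproduces the stated 30 per group (80% power, two-sided 5%, 5% losses). It concerns the theory-of-mind stories only; the documents give no sample size or power for work results.

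**2. Evaluable patients.** The planned total is 80. With 1:1 allocation (assumed; the ratio is not stated) and the same 5% losses, 40 × 0.95 = 38 per arm.

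**3. What the mixed model offers.** The group-by-time effect is (post − pre) in the experimental arm minus (post − pre) in the control arm. With every pre value set to zero, this is the difference in post means. On one simulated data set with 40 per arm, the mixed model gave 59.2 (SE 85.8) and the post-only t-test gave 59.2 (SE 85.8). The model adds nothing.

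**4. What a baseline covariate can offer.** Adjustment multiplies the variance of the arm difference by about 1 − r², where r is the correlation of the covariate with the outcome. The documents give no r. A correlation of 0.3 to 0.6 with the latent propensity to work implied r of 0.12 to 0.41 with hours in simulation:
- r = 0.12: 1 − 0.0144 = 0.986, a 1% reduction in variance.
- r = 0.41: 1 − 0.168 = 0.832, a 17% reduction.

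**5. Power for obtained work (yes/no), 38 per arm.** With p̄ the mean of the two proportions, power = Φ{[|p₁ − p₂| − 1.96√(2p̄(1 − p̄)/n)] / √([p₁(1 − p₁) + p₂(1 − p₂)]/n)}.
- 30% vs 60%: (0.300 − 1.96 × 0.1141)/0.1088 = 0.70, power 76%.
- 20% vs 50%: (0.300 − 1.96 × 0.1094)/0.1039 = 0.82, power 79%.

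Simulation (4,000 trials per setting) gave 74% to 81% unadjusted and 78% to 88% adjusted. A second run of the same model (1,500 trials per setting) gave 77% to 89% adjusted, with gains of about 1 to 3 points at correlation 0.3 and 8 to 10 at 0.6.

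**6. Power for hours.** With gamma-distributed hours among workers (CV 0.4 to 1.2), never-workers as zero and 38 per arm, adjustment added 0 to 9 points. A separate model used lognormal hours, 40 per arm, 30% vs 60% employed and 2,500 trials per cell:

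| Log-SD of workers' hours | Latent correlation | t-test | Adjusted | Gain (points) |
|---|---|---|---|---|
| 0.4 | 0.3 | 67.7% | 68.7% | 1.0 |
| 0.4 | 0.5 | 68.0% | 72.9% | 4.9 |
| 0.4 | 0.7 | 68.2% | 78.5% | 10.3 |
| 0.7 | 0.3 | 50.8% | 51.2% | 0.4 |
| 0.7 | 0.5 | 48.3% | 50.4% | 2.1 |
| 0.7 | 0.7 | 49.8% | 56.2% | 6.4 |
| 1.0 | 0.3 | 36.0% | 36.5% | 0.5 |
| 1.0 | 0.5 | 35.4% | 36.3% | 0.9 |
| 1.0 | 0.7 | 34.3% | 37.4% | 3.1 |

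The gain shrinks as workers' hours become more skewed, because the baseline score then explains less of the spread.

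**7. Type I error.** It was 3% to 5% for all methods in the gamma simulations, and 3.8% to 5.6% for the t-test in the lognormal ones.

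**The case against.** The strongest reply is that the gain is small and rests on a correlation nobody has measured. The SAP also never says that the t-test is meant for work results: its sentence on that test is incomplete, and the conclusion is reached by elimination. All of this stands. If the elimination is rejected, however, work results have no stated analysis at all, and the same SAP paragraph is still needed. The lack of baseline hours and pay is likewise inferred from silence.

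Three stronger readings are tempting, and the documents do not support them.

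- A reader might infer that no work measure has a pre value. The SFS employment/occupation score has both pre and post values and fits the mixed model as it stands.
- A reader might set the t-test on hours (32% to 71% power under the gamma assumptions) against the comparison of proportions employed (74% to 88%) and conclude that the named test would miss an effect on getting work. That contrast mostly changes the outcome, not the test. The SAP's own t-test applied to obtained work, yes/no, has about 76% to 81% power. Nor is the proportion a safe lead outcome. With 40% vs 60% employed and 1.3 times the hours among workers, the proportion has 42% power against 71% for hours; with 40% vs 55% and 1.5 times the hours, 26% against 70%; with equal employment and doubled hours, 6% against 49%. Which to lead with is a choice of estimand.
- A reader might infer that zeros and skew, or Levene's test rejecting in 25% to 28% of null trials, make the t-test invalid. Type I error stays close to 5%, and Student and Welch versions differed by at most 0.6 points of power. Skew can cost power, but how much depends on employment rates and spread that the documents do not give.

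**Conclusion.** The point holds as a modest improvement to a secondary analysis. Neither method named in the SAP uses baseline information for hours, maintenance or salary, although a relevant baseline score is collected from both arms. The size rests on assumed employment rates, an assumed distribution of hours and an assumed correlation; only the 38 per arm is tied to the plan's own total and loss rate. If the baseline score barely varies, for example because almost nobody is working at entry, the gain disappears. Entry does not require unemployment (Protocol 4.2.1), so the spread of this score cannot be predicted from the documents.

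**What to change.** Add a short paragraph to the SAP:

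- Compare each work result (obtained work yes/no, hours, salary, with never-workers counted as zero) between all randomised patients by regression on arm, adjusted for the pre-evaluation SFS employment/occupation score. Report the adjusted difference with a robust or bootstrap 95% interval, in place of the unadjusted t-test. Job maintenance can be handled in the same way once it is defined.
- Analyse the SFS employment/occupation score itself in the pre/post mixed model.
- The SAP expects some patients to lack pre or post data, so state how a missing baseline score is handled. Keep patients whose work status is unknown separate from those known not to have worked.

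The cost is a paragraph and a little programming, with no new data collection. The result is read as an adjusted difference. The comparison of hours and salary remains one of means, so robust or bootstrap intervals do not recover power lost to skew.
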